A subset of kebeles (n=70) was randomly allocated to Ifaa Basic and Ifaa Enhanced Packages as part of a cross-RFSA learning activity (USAID is supporting similar projects in other regions of Ethiopia) that is supported by the funder, USAID Bureau of Humanitarian Affairs. This effectiveness evaluation leverages this randomization to compare the two intervention packages. Additionally, 50% of kebeles were selected for livelihoods interventions, which occur in both Basic and Enhanced kebeles; livelihoods kebeles were selected based on criteria developed by CRS, but assignment to the enhanced vs basic package was random. Finally, approximately half of Ifaa Project kebeles are 'the free zone' where there is flexibility in intervention packages of the course of the project.¹ The distribution of the three Ifaa intervention packages that will compare in the proposed effectiveness evaluation is presented in **Table 2** below.

Table 2: Ifaa Intervention Allocation by Administrative Area

| Woredas/Districts Intervention Package | Study Eligible Kebeles/Sub-Districts* | | |
|---|---------------------------------------|---|--|
| | Ifaa Basic (n=25) | Ifaa Enhanced (n=34) | Ifaa Enhanced + Livelihoods (n=35) |
| Babile | Gemechu Ifa Jalale | Lekolo Shek husen Tofiq Tuluhoro | Erer guda Gambela Ibada gemechu Nejata gemechis |
| Chinaksan | Chelchale Kobobika | Biftuu Waree Gela | Amola Baduelemo |

¹ These kebeles were not considered in the sampling frame because of the high risk of contamination.

| | Migira | Kaleroga | Dawe kora |
|-------------|---|--|---|
| | Tiro gudoo Wachuhulet | Orda sost Tirosendare | Dembesele Kocher Merer Mudi dawe |
| Deder | Burka Berekha Mumicha Nedi gelansedi | Gegewisa Haremlemekuni Huffe Kura deder Lemen welteha | Burka Geba Cheka gemechu Chela Negeya Golu Oda kebena Welteha gudina |
| Fedis | Bareda Bedatu | Bid Borra Efitu dada Negaya bobasa Risiki | Ido Baaso Kerensa lencho Umer kule |
| Gursum | Ebsa Hariro Misira Saqabadii | Berite Gara wadaja Gefire guda Goro siyo Kebso Negeya | Awdal Day feres Harashi Kasa oromiya Oda oromiya |
| Jarso | Aneno mite Burka mete Debub debelo | Amen Epa jalela Gidiya licha Oda muda | Afgug Chala Gara abdula |
| Melka Belo | Fule negeya Haka mulisi Tokuma bilisumu | Bifitu negeya Daba kenisa Mulisa hakwa Tokuman kane | Chefe Jeneta Dire Qufa Welikituma bilusuma |
| Midega Tola | Ibiro musa Terkafeta | Kerensa Mukura | Bilisuma Biyo waraba Lencha Roba |

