As noted in Figure 1, the study includes three of the possible four Ifaa intervention combinations. Characterizing the impact of livelihoods programming without the Ifaa enhanced intervention was not considered a priority.

Figure 2. Study Flow Diagram

A longitudinal cohort design will be used to compare the effectiveness of three Ifaa intervention packages among PSNP beneficiaries: 1) the Ifaa basic package; 2) enhanced package without livelihoods; and 3) enhanced package with livelihoods. Under this approach, the enrolled households will have either a pregnant woman or children <36 months of age. Households will be followed over a two-year period, with the baseline and endline survey conducted at a similar time

³ Community led complementary feeding sessions (CCFLS) is a six month program targeted at children at risk of acute malnutrition or recently discharged from a malnutrition treatment program. It includes caregiver training on child feeding practices and growth monitoring and is a six month intervention, with intensive services/training in the first month and follow up monitoring.

period in the calendar year to avoid seasonal changes in food security. The magnitude of change in key indicators over time will be assessed for each group; if needed, adjusted models will be used to account for baseline differences between groups. Outcome measures of focus are aligned with Ifaa indicators and include measures of household food consumption and child diet. To ensure adequate geographic coverage, a **stratified sampling design** will be used as follows:

- (1) **Kebele Selection.** Two kebeles per intervention arm will be purposively selected in each of the nine woredas with the aims of 1) of maximizing geographic similarity in terms of agro-ecological zone (lowland, midland, highland) and remoteness; and 2) ensuring sufficiently large beneficiary population is available for sampling purposes. In the case of smaller kebeles where it appears unfeasible to attain three clusters, the sample may be distributed across additional kebeles within the woreda.⁴

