- (2) **Cluster Selection.** Within each kebele, the three largest communities and/or population concentrations from within each kebele will be selected as cluster start locations. This approach was identified to account for inclusion criteria, notably that households must have a pregnant woman or a child <36 months of age, which reduces the number of households that are eligible for study participation.⁵ Once start locations have been identified, all beneficiary lists will be verified, and households that meet inclusion criteria will be enumerated. This process will occur immediately prior to the start up of data collection in the kebele. If fewer than 20 eligible households are identified in the community, enumeration will continue in adjacent communities until the target sample size is identified.
- (3) **Household Selection.** Data collection will begin within several days of the household enumeration exercise. Households will be sampled from the lists of beneficiaries that are verified as meeting inclusion criteria. In some cases, this may be exhaustive (e.g. in kebeles with small populations where adjacent communities needed to be visited to identify the target number of households). In larger kebeles or communities where the number of eligible households exceeds the target sample, a systematic list-based sampling approach (i.e. every n^{th} household) will be used. Replacement sampling will be used until the target number of households in each location are enrolled.

B. Sample Size

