The outcome variables of focus at the household level will be measures of food security, including 1) [Food Consumption Score](#), 2) [Household Hunger Scale](#), and 3) [Coping Strategies Index](#). At the individual level, outcome variables of focus will include 1) [Infant and Young Child Feeding Indicators](#) (in particular achievement of minimum dietary diversity); and 2) prevalence of stunting and wasting, in accordance with the [World Health Organization Child Growth Standards](#). Background information on individual (e.g. literacy, age, pregnancy status) and household characteristics (e.g. size, residence location) will also be collected so that these can be controlled for or used for disaggregation in data analysis. All outcomes will be analyzed as continuous variables and as categorical variables based on pre-determined thresholds.

A descriptive analysis of household sociodemographic characteristics and outcome measures will be performed. Continuous variables will be presented as mean (SD) and categorical variables as n (%). ANOVA tests will be conducted for baseline characteristics and primary and secondary outcomes to examine the comparability between the three and intervention groups; individual/household characteristics with significant differences between groups at baseline will be controlled for in models that estimate the effect of the interventions.

The program effect on expected primary outcome measures will be estimated using mixed-effect linear regression analysis for continuous outcomes and Generalized Estimation Equation (GEE) model for binary outcomes. In the mixed-effects models, the random effect component included indicators to control for clustering at school levels. The fixed component included the intervention group (intervention vs. control), time and an interaction term for group and time. The GEE models will be used to examine binary outcomes with longitudinal data from both enrollment and endline. These models will estimate the change in a binary outcome among members of a given intervention group from enrollment to endline, compared to the change in the same outcome in the control. The GEE models also included an interaction term between the intervention group and time (baseline/endline).

5. **Answer the following if they are relevant to your study design:**

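### GEE for the two sizing outcomes has no stated cluster or small-sample correction; with 16–18 kebeles per arm, default inference would reject about 6–7% at a nominal 5%

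*Combined protocol and SAP*

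**What the plan says.** Section V.C.3 specifies mixed-effects linear regression for continuous outcomes and a "Generalized Estimation Equation (GEE) model for binary outcomes". The GEE contains intervention group, time and their interaction, so the effect tested is the difference in change between an intervention group and the comparison group. The only clustering statement concerns the mixed models, where "the random effect component included indicators to control for clustering at school levels". No cluster, working correlation, variance estimator, reference distribution or small-sample correction is given for the GEE.

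The number of kebeles comes from Section III.A. Item (1) states that "Two kebeles per intervention arm will be purposively selected in each of the nine woredas". It adds that, where a kebele is too small for three clusters, "the sample may be distributed across additional kebeles within the woreda". Item (2) says that "the three largest communities and/or population concentrations from within each kebele will be selected as cluster start locations", with a target of 20 eligible households per community. Section III.B sets alpha at 0.05 and plans 1,080 households per group. Table 2 in Section II lists eight woredas and gives 25 eligible Basic kebeles.

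**The concern.** A contrast between two packages involves about 2,160 households but only 32–36 independently assigned units. The ordinary GEE sandwich variance is justified by a large number of clusters. With 16–18 per arm it is biased downward, because residuals are measured from means fitted to the same few kebeles. The usual normal reference also ignores the uncertainty in that variance. Both errors make tests too liberal and intervals too short.

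At stake is whether the stated alpha of 0.05 is delivered for the two outcomes that determine the sample size. Naming the kebele as the cluster would not settle this, because the shortfall remains after the correct cluster is chosen.

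**Working it through.** **Inputs from the plan.** Two kebeles per arm per woreda, nine woredas in the text and eight in Table 2 (III.A, II); three clusters of 20 households per kebele (III.A); alpha 0.05, 20% loss (III.B); baseline prevalences 34% or 48% for food consumption and 19.5% for dietary diversity (Table 3).

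**Reproducing the plan's figures.**
- 9 woredas × 2 kebeles × 3 clusters × 20 households = 1,080 per group, exactly the planned number. So 18 kebeles per arm is the design behind the sample size. Eight woredas would give 8 × 2 = 16.
- A two-sided 5%, 80%-power comparison of two proportions, × 1.5 for the design effect and × 1.2 for loss, gives 926, 1,088 and 792 for the three 8-point rows of Table 3. The plan has 915, 1,070 and 785. The agreement supports reading alpha as two-sided.

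**Analytic size, equal kebele sizes.** With K kebeles per arm, the uncorrected sandwich is about (K−1)/K times the unbiased between-kebele variance. The reported z is then a t statistic on 2(K−1) degrees of freedom multiplied by √(K/(K−1)), and the rejection probability is

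P( |t with 2(K−1) df| > 1.96 × √((K−1)/K) ).

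| K per arm | df | Threshold on the t scale | Actual size |
|---|---|---|---|
| 16 | 30 | 1.96 × √(15/16) = 1.898 | 6.7% |
| 18 | 34 | 1.96 × √(17/18) = 1.905 | 6.5% |
| 25 | 48 | 1.96 × √(24/25) = 1.920 | 6.1% |

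This approximation needs no intracluster correlation.

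**Simulation, equal sizes.** Three arms, logit GEE with independence working correlation, clustered on kebele, 60 households per kebele, 20% loss, prevalence 48% or 19.5%. The kebele and kebele-by-time variances on the logit scale were assumed (0.01/0.01 and 0.05/0.03). One pairwise interaction was rejected 6.0–7.0% of the time at 16–18 kebeles per arm (Monte Carlo standard error about 0.3–0.4 points).

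**Simulation, overflow into extra kebeles.** Kebele samples were capped at 60 and split as overflow would split them. Assumed logit-scale SDs were 0.10 (kebele), 0.15 (kebele-by-time) and 1.0 (household).

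| Kebeles per arm | CV of kebele sample size | Size |
|---|---|---|
| 20–21 | 0.28–0.33 | 6.5% |
| 23 | 0.35–0.40 | 6.3% |
| 25 | 0.17–0.39 | 6.1% |

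**After correction.** Rescaling the variance by K/(K−1) and using t with 2(K−1) degrees of freedom gave 4.6–5.2% with equal sizes at 16–18 kebeles per arm. A leverage-corrected sandwich with a t reference gave about 5.0–5.4%.

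**Interval widening.**
- K = 18: (2.032/1.960) × √(18/17) = 1.067.
- K = 16: (2.042/1.960) × √(16/15) = 1.076.
- K = 25: (2.011/1.960) × √(25/24) = 1.047.

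**The case against.** The strongest reply is that V.C.3 is a short answer to an ethics-board template and does not say which inference it will use. That stands. A reader might infer that the plan commits to large-sample inference, but its silence does not support this, so the finding must be conditional. The silence still matters: the named method run with its usual defaults gives intervals that are too short, and nothing commits the analyst to anything better before the endline data are seen.

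A reader might also infer a larger error, 8% or more, from footnote 4, which puts beneficiary households at about 75 to 650 per kebele. With K held at 16–18 and an assumed CV of kebele sample size of 0.4, simulation does give 6.9–8.0%. But the documents give no such CV. Sampling is held to about 60 per kebele by three clusters of 20, with systematic selection where more are eligible, and III.B foresees only a few extra households in a kebele. Uneven sizes would arise mainly when clusters move to additional kebeles, which raises K. A reader might infer that this overflow makes matters worse; the overflow runs above (6.1–6.5%) do not show that.

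Finally, the unnamed GEE cluster is the larger risk. Clustering on household rejected about 8–22% under the assumed variances. That is true, but it is a different defect, and curing it leaves this one in place.

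**Conclusion.** The point holds in conditional form. If the GEE is run with an uncorrected sandwich and a normal reference, clustered on kebele, a nominal 5% test of one package-by-time contrast rejects about 6–7% of the time, and 95% intervals cover about 93–94%. The analytic figure rests on equal kebele sizes and an approximately normal kebele-level change; the simulated figures rest on the assumed variances given above. More kebeles bring the size nearer 6%, and even all 25 Basic kebeles, matched by 25 in the other arm, leave it at about 6.1% analytically. The effect is modest, but a standard and inexpensive method removes nearly all of it.

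**What to change.** In V.C.3, state that GEE tests and confidence intervals for the binary outcomes cluster on kebele and use a bias-corrected sandwich variance (for example Kauermann–Carroll). State also that they use a t reference whose degrees of freedom, for each pairwise contrast, equal the number of kebeles in the two compared arms minus 2: 32 − 2 = 30 to 36 − 2 = 34 under the base design, and more if overflow kebeles are used. The pairwise count should be explicit, because counting all 54 kebeles minus three arm parameters would give 51, which is not the reference checked here.

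The cost is one sentence and a standard software option, with no change to sampling or fieldwork. Intervals become about 7–8% wider at 16–18 kebeles per arm and about 5% wider at 25, with a corresponding small loss of power.

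### The mixed model clusters on schools, which are not a unit of this trial, and the GEE for the binary sizing outcomes names no cluster unit although packages are assigned by kebele.

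*Combined protocol and SAP*

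**What the plan says.** Section V.C, item 3 (data analysis plan) assigns continuous outcomes to a mixed-effects linear model and binary outcomes to a GEE.

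- **Mixed model.** The clustering statement is "the random effect component included indicators to control for clustering at school levels". The fixed part is given as "The fixed component included the intervention group (intervention vs. control), time and an interaction term for group and time".
- **GEE.** The plan says "The GEE models will be used to examine binary outcomes with longitudinal data from both enrollment and endline" and adds a group-by-time interaction. It gives no cluster unit, working correlation or level for the robust variance.

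The design sections describe different units.

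- **Assignment** (Section II): "A subset of kebeles (n=70) was randomly allocated to Ifaa Basic and Ifaa Enhanced Packages".
- **Kebele selection** (Section III.A): "Two kebeles per intervention arm will be purposively selected in each of the nine woredas". For small kebeles, "the sample may be distributed across additional kebeles within the woreda".
- **Sampling within kebeles** (Section III.A): "the three largest communities and/or population concentrations from within each kebele will be selected as cluster start locations". Households are then drawn from verified lists.
- **Sizing** (Section III.B): the design effect of 1.5 is there to allow for kebele differences. Both sizing outcomes are binary: poor or borderline Food Consumption Score, and minimum dietary diversity in children under 5.

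Schools appear only in Table 1, as settings for some Enhanced activities.

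**The concern.** Households qualify through a pregnancy or a child under 36 months (Section IV.A). Child data cover children under 5, and visits take place at the residence (Section V.C). The described procedures record no school, so the random effect as written has no variable behind it.

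The GEE gap matters more, because that model produces the effect estimates for both sizing outcomes. The only structure it mentions is the two time points, so the most natural reading is that the household is the repeated-measures cluster. On that reading the analysis leaves out the kebele correlation that the sample size paid for.

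Section III.A offers kebele, community and household as candidates. The group-by-time standard error can come out too small or too large, depending on which one the analyst picks.

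**Working it through.** **1. Sizing does allow for kebeles.** A pooled two-proportion calculation (two-sided 0.05, 80% power), multiplied by 1.5 for design and 1.2 for loss, gives the following. Rows were matched to baselines by inference, because Table 3 is broken in the text.

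| 8-point change | Calculation | Plan |
|---|---|---|
| 34% to 26% | 514 × 1.8 = 926 | 915 |
| 48% to 40% | 604 × 1.8 = 1,088 | 1,070 |
| 19.5% to 27.5% | 440 × 1.8 = 792 | 785 |

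All agree within 3%, so the design effect is in the plan's figures.

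**2. Inputs.**

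- From the documents: 2 kebeles × 9 woredas = 18 kebeles per arm; 1,080/18 = 60 households each; 20% loss leaves m = 48.
- ICC implied by design effect 1.5: 0.5/47 = 0.0106. ICC 0.05 would mean a design effect of 1 + 47 × 0.05 = 3.35.
- Assumed, because the documents are silent: kebele autocorrelation between rounds (CAC) 0.8; household correlation between rounds (IAC) 0.2-0.4.

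**3. Household term but no kebele term.** Variance factors for the change, per household:

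- True: 2[m·ICC(1−CAC) + (1−ICC)(1−IAC)]
- Model: 2[ICC(1−CAC) + (1−ICC)(1−IAC)]
- Type I error: 2(1−Φ(1.96·√(model/true)))

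Example at ICC 0.0106, CAC 0.8, IAC 0.3: true = 2[0.1021 + 0.6926] = 1.589; model = 2[0.0021 + 0.6926] = 1.389; type I error = 6.7%.

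| ICC | CAC | IAC 0.2 | IAC 0.3 | IAC 0.4 |
|---|---|---|---|---|
| 0.0106 | 0.8 | 6.5% | 6.7% | 7.0% |
| 0.05 | 0.8 | 12.2% | 13.2% | 14.5% |
| either | 1.0 | 5.0% | 5.0% | 5.0% |
| 0.0106 | 0.5 | 8.7% | 9.3% | 10.0% |
| 0.05 | 0.5 | 21.5% | 23.3% | 25.6% |

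**4. Kebele intercept but no household term** ('school' read as 'kebele', nothing added). The model factor is 2[(1−ICC)(1−IAC) + (1−ICC)·IAC·2(m−1)/(2m−1) + ICC(1−CAC)·m/(2m−1)]. At IAC 0.3:

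- ICC 0.0106, CAC 0.8: √(1.975/1.589) = 1.115, so the SE is about 12% too large.
- CAC 1.0: ratio 1.193, about 19% too large.
- ICC 0.05, CAC 0.8: √(1.904/2.290) = 0.912, about 9% too small.

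**5. Binary check.** 10,000 simulated two-arm trials with a 48% outcome in both rounds, logit GEE, independence working correlation and IAC 0.3. The correction scales the variance by K/(K−1), with K kebeles per arm, and uses t with 2K−2 df.

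| 18 kebeles × 48 | Household clusters | Kebele, uncorrected | Kebele, corrected |
|---|---|---|---|
| ICC 0.0106, CAC 0.8 | 6.9% | 6.8% | 5.1% |
| ICC 0.0106, CAC 1.0 | 5.0% | 6.5% | 5.2% |
| ICC 0.05, CAC 0.8 | 13.2% | 6.5% | 5.0% |

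A kebele-level normal check with 200,000 runs gave 6.4% uncorrected and 4.9% corrected.

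**6. More kebeles.** The Section III.B footnotes give 75-650 beneficiary households per kebele, 15-25% of them eligible: 75 × 0.15 = 11 to 650 × 0.25 = 163. Finding 60 eligible households needs 60/0.25 = 240 to 60/0.15 = 400 beneficiary households, so spread beyond 18 kebeles is possible. Table 2 lists 25 Basic kebeles. At 25 per arm, m = 864/25 = 34.6 and CAC 0.8, household-only error is 6.0-6.4% at ICC 0.0106 and 10.2-11.9% at ICC 0.05. In the kebele-level normal check, 25 per arm gave 6.1% uncorrected and 5.0% corrected.

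**The case against.** **It is a slip with recoverable intent.** Nobody can fit a school effect without school data, so an analyst would turn to kebele or community. That is fair for the mixed model. However, reading 'kebele' for 'school' still leaves a model without a household term, whose standard error is off in one direction or the other, and it does nothing for the GEE.

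**The form asks only for a brief plan, and household-only clustering is a reading of it.** True. But the cluster unit in a cluster-assigned study is not a detail, and no other section supplies it.

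**The sizes are driven by assumptions.** This stands. CAC 0.8 is one scenario. At that value the variance inflation of the change is only 1.13-1.17, not 1.5, and CAC 0.5 gives clearly larger errors. The ICC 0.05 case needs more than twice the plan's design effect. The scale of the ICC matters too: with the same values on the latent scale, a separate simulation gave household-clustered error of about 5.7% and 9.9%.

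**Naming kebele alone gains little at the planned design effect.** Also true: 6.8% against 6.9%. The small-sample correction is what restores 5%.

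**Woreda stratification is ignored.** The calculations treat kebeles as unstratified, so they do not mirror the design exactly. This does not supply a cluster unit.

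**Power is left out.** At ICC 0.05, CAC 0.8 and IAC 0.3, with 864 completers per arm, the SE of a between-arm difference in change from 48% is √(2 × 0.48 × 0.52 × 2.290/864) = 0.036. Power for 8 points is then about 59%. Correct standard errors reveal that loss; they do not cause it.

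**Conclusion.** The point holds: the analysis plan is wrong as written for the mixed model and silent for the GEE, and it should be fixed. Both textual findings rest on the documents alone.

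The size is illustrative. At the design effect the plan itself uses, the inflation from household-only clustering is modest. It becomes serious only if kebeles differ more than planned or drift more between rounds, and it vanishes if kebele effects are fully stable over the two years. Confidence in the defect is high. Confidence in any single error rate is limited, because the ICC, CAC and IAC are all assumed.

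**What to change.** In Section V.C, item 3:

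- Replace the school term with kebele. Fit the mixed model with random effects for kebele, kebele-by-round and household, with children nested in household for child outcomes.
- State that the GEE is clustered on kebele with robust standard errors. This also covers the community clusters, which are nested in kebeles.
- Specify a small-sample correction for the GEE, because only about 18 kebeles per arm are planned.
- As a clarification, code group in both models as the three-level factor in Section V, item 5.A. List Enhanced + Livelihoods versus Enhanced beside the two contrasts with Basic.

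The cost is wording, provided it is done before the May 2025 endline data are analysed. Planned N does not change. The price is a somewhat more complex model and, in some cases, slightly wider intervals. Section VI, item 4 deletes unique identifiers after endline, so coded kebele and household IDs need to stay in the de-identified analysis file.

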The primary outcome measure for the evaluation is improvement in household food security. To align the evaluation with project aims, key project indicators are used as study outcome measures. These include: 1) At the household level, **Poor or Borderline Food Consumption Score (FCS)**; and 2) at the individual level, change in **minimum dietary diversity among children <5 years**. Sample size calculations are presented in **Table 3** (following page) and are based on both primary and secondary outcome measures for within-group change over time using available data from the Ifaa baseline along with Ifaa targets for change. Assumptions included the following: 1) power ($1-\beta$) of 80% and significance of $\alpha=0.05$; 2) a design effect of 1.5 to take into account differences across Kebeles; and 3) expected absolute change in proportion of primary/secondary outcome; and 4) loss to follow up rate of 20% over the study period. Based on initial sample size projections, a minimum sample size of 915-1,070 households per group and 2,745-3,210 is required which is sufficient to detect differences $\geq 8\%$ between groups for both the primary and secondary outcome measures.

We are proposing a planned sample size of 1,080 per group or 3,240 households total. Given challenges in field coordination across multiple teams and delays in data quality monitoring reviews, it is possible that several additional households could be enrolled in a kebele. To ensure that the approved sample size is not inadvertently exceeded due to communication challenges we are requesting approval for a **maximum sample of 3,500 households**.

Table 3: Sample Size Calculations

| | Baseline Value | Magnitude of Change | Sample Size per Group | Total Sample Size |
|--|----------------------------|---------------------|-----------------------|-------------------|
| | 34% in Oromiya (WFP, 2021) | -8% | 915 | 2745 |

⁴ The number of beneficiary households per kebele ranges from approximately 75 to 650; given inclusion criteria it is unlikely that smaller kebeles will have 60 eligible households, in which case cluster(s) will be assigned in additional kebeles in the woreda.

⁵ In the baseline survey, the average number of children <5years in PSNP households was 0.83 and 14% of the population was <5 years of age. Based on this we estimate that 15-25% of Ifaa beneficiary households will meet study inclusion criteria.

| | | | | | |
|---|---|-------|------|------|--|

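### The mixed model for continuous outcomes names one random-effect level; relabelling it from school to kebele would still leave the group-by-time standard error wrong, in a direction the documents do not settle

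*Combined protocol and SAP*

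**What the plan says.** The analysis plan in section V.C, item 3, assigns "mixed-effect linear regression analysis for continuous outcomes and Generalized Estimation Equation (GEE) model for binary outcomes". For the mixed model it states that "the random effect component included indicators to control for clustering at school levels" and that "The fixed component included the intervention group (intervention vs. control), time and an interaction term for group and time". The group-by-time term is therefore the package effect. Nothing further is said about the covariance: no household term, no kebele or kebele-by-time term, no residual correlation, no robust variance and no small-sample degrees of freedom.

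The design sections describe something else. Section III.A says "A longitudinal cohort design will be used to compare the effectiveness of three Ifaa intervention packages among PSNP beneficiaries", with the same households surveyed at baseline and again at 24 months. Section II says "A subset of kebeles (n=70) was randomly allocated to Ifaa Basic and Ifaa Enhanced Packages", so the kebele is the unit that receives a package. Section III.A adds "Two kebeles per intervention arm will be purposively selected in each of the nine woredas", and within each kebele "the three largest communities and/or population concentrations from within each kebele will be selected as cluster start locations". There are no schools in the design. Section III.B allows for "a design effect of 1.5 to take into account differences across Kebeles", but only as a multiplier in the sample size.

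**The concern.** The obvious repair is to replace the school label with kebele. That corrects the name but not the standard error. In a two-round cohort a kebele intercept adds the same amount to baseline and endline, so it drops out of the change and out of the group-by-time contrast. Two things then remain wrong.

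- Kebeles may change by different amounts for reasons unrelated to the package. That variation sits at the level where packages are delivered, and the model does not carry it. This makes the standard error too small.
- A household's two values are treated as independent given the kebele, so the stable household component is counted as noise. This makes the standard error too large.

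The two errors pull in opposite directions and cancel only by coincidence. At stake is whether the package effects on continuous measures, such as the Food Consumption Score analysed as a score, carry p-values and intervals of the stated size.

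**Working it through.** **Inputs from the documents.** Two kebeles per arm in each of nine woredas gives K = 18 per arm. The planned 1,080 households per group give 1,080/18 = 60 per kebele, or m = 60 × 0.8 = 48 after the planned 20% loss. The design effect is 1.5, alpha 0.05 and power 80% (section III.B).

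**The plan's own figure.** A two-sided comparison of 34% with 26% needs 514 per group, and 514 × 1.5 × 1.2 gives 926, against 915 in Table 3. For 48% against 40%, 604 × 1.5 × 1.2 gives 1,088, against 1,070. So the design effect enters the sample size as a plain multiplier and does not inform the model.

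**Implied ICC.** From 1 + (60 − 1) × ICC = 1.5, ICC = 0.5/59 = 0.0085. If the cluster is read as a community of 20, it is 0.5/19 = 0.026.

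**Assumptions.** The documents give no household correlation over time and no split of the kebele variance. Set the total variance to 1. Let v be the kebele-by-time variance, h the household variance, e the residual variance, and r the household share of the within-kebele variance.

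**Formula.** For two arms compared:

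- true variance of the group-by-time estimate: 4(v + e/m)/K
- variance reported with a kebele intercept only: approximately 4(v + h + e)/(Km)
- ratio: R = (m·v + e)/(v + h + e)
- size of the nominal 5% test: 2[1 − Φ(1.96/√R)]

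K cancels from R. R equals 1 only if v = h/(m − 1).

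**One case in full.** Take ICC 0.0085, half of it kebele-by-time, r = 0.5. Then v = 0.00425 and h = e = 0.49575. R = (48 × 0.00425 + 0.49575)/0.99575 = 0.69975/0.99575 = 0.70, and size = 2[1 − Φ(2.34)] = 1.9%.

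**Kebele intercept only, m = 48 (R, size):**

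| ICC | Kebele variance that is kebele-by-time | r = 0.4 | r = 0.5 |
|---|---|---|---|
| 0.0085 | none | 0.60, 1.1% | 0.50, 0.6% |
| 0.0085 | half | 0.80, 2.9% | 0.70, 1.9% |
| 0.0085 | all | 1.00, 5.0% | 0.90, 3.9% |
| 0.02 | half | 1.08, 5.9% | 0.98, 4.8% |
| 0.02 | all | 1.55, 11.5% | 1.45, 10.4% |
| 0.05 | half | 1.82, 14.6% | 1.72, 13.5% |
| 0.05 | all | 2.97, 25.5% | 2.88, 24.8% |

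With r = 0, ICC 0.0085 and all of it kebele-by-time, R = 1.40 and size is 9.8%. At R = 0.50 the reported standard error is 1/√0.50 = 1.41 times the true one, which is the power cost at the conservative end.

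**Adding a household intercept but no kebele-by-time term.** The ratio becomes (m·v + e)/(v + e). At ICC 0.0085 the size is 9.0% (r = 0.4) and 9.8% (r = 0.5) with half of the kebele variance kebele-by-time, and 12.8% and 14.3% with all of it.

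**Simulation check.** With 18 kebeles per arm, 48 households, r = 0.5 and 4,000 runs per scenario, the kebele-intercept test had size 0.5% (ICC 0.0085, none), 2.0% (ICC 0.0085, half) and 14.5% (ICC 0.05, half). Fitting the mixed model itself in 400 runs gave 15.3% in the last case. Testing kebele-level mean changes with 2 × 18 − 2 = 34 degrees of freedom held size at 4.3% to 5.3% in every scenario.

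**The case against.** The strongest reply is that the plan is silent rather than wrong. It is a brief plan in an ethics form. It never says that the cluster intercept is the only random effect, and since there are no schools the sentence cannot be run as written. That stands: a reader might infer that the plan rules out a household term, and it does not. The single intercept is the natural reading, not the literal text. But naming the kebele alone would leave the gap open.

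A reader might also infer that the type I error is inflated. The documents do not support that. At the ICC implied by the plan's own design effect, with moderate household correlation, the test is conservative to nominal. The 9.8% figure needs zero household correlation over two years in the same households and kebele effects that do not persist at all. Nor do the 9% to 14% figures describe this plan; they describe a partial repair that it does not propose.

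Third, the measures used for the sample size, poor or borderline food consumption and minimum dietary diversity, are binary and go to GEE. Nothing here shows that those comparisons are mis-sized. Applying the mixed model to child growth scores is also an inference, because the plan ties these models to the primary outcome measures.

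Finally, the number of kebeles may differ from 18 per arm, since the footnote on small kebeles allows extra ones. This does not change R, though unequal kebele sizes make the closed form approximate.

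**Conclusion.** The point holds as a fault of specification with a real consequence. On its natural reading, the model for continuous outcomes gives a wrong standard error for the group-by-time term even once the cluster is correctly named, except where v happens to equal h/(m − 1).

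With 48 households per kebele, the size of the nominal 5% test is:

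- about 0.6% to 5% at ICC 0.0085 and household correlation 0.4 to 0.5, where a significant result would be safe and the cost is power;
- up to about 10% at that ICC with no household correlation;
- about 5% to 25% at ICC 0.02 to 0.05 and household correlation 0.4 to 0.5, if half or more of the kebele variance is kebele-by-time.

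ICC values other than 0.0085, the household correlation and the kebele-by-time share are assumptions. Even 0.0085 relies on reading the design effect at 60 per kebele. The direction therefore cannot be stated in advance.

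**What to change.** When the cluster unit is corrected, state the whole covariance structure in the same sentence:

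- random effects for kebele, kebele-by-time and household, plus child for outcomes measured twice on the same child;
- group-by-time tested with Satterthwaite or Kenward-Roger degrees of freedom based on kebeles.

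Both the household and the kebele-by-time terms are needed, because the household term alone exposes the missing kebele-level variation. An analysis of kebele-level mean change is a useful sensitivity check. It is equivalent to the mixed model only with balanced, complete data, which attrition, covariate adjustment and unequal kebeles make unlikely.

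The cost is analysis-plan wording; no extra data are needed. The downside is that intervals may widen where kebeles change at different rates.
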